**OBJECTIVES:**

**Purpose**

The primary purpose of the study is to determine the effect of sleep deprivation on neural responses to food odors in the early olfactory and reward-related brain regions, and how these effects are related to appetite-regulating hormones. We will further examine how altered neural responses to food translate to enhanced appetite and food intake, and which brain processes support resilience to sleep-dependent increases in food intake. We will use appetitive food odors in combination with functional magnetic resonance imaging (fMRI) and pattern-based data analysis to test the effects of sleep deprivation on neural responses to food. We will also examine effects of sleep deprivation on appetite levels, odor pleasantness, and *ad-libitum* calorie intake.

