**Specific aims and Hypothesis**

**Aim 1. Identify sleep dependent alterations in early olfactory responses to food odors.**

Food odors reliably activate both early olfactory and reward-related brain networks. Orexigenic hormones are enhanced in a sleep-deprived state and have been shown to modulate olfactory sensitivity to food. Here we aim to identify effects of sleep deprivation on early sensory processing of food odors, and how these effects are linked to changes in appetite-regulating hormones. *We hypothesize that fMRI responses to high-caloric food odors will be elevated when subjects are sleep-deprived. Specifically, we predict that sleep-deprivation will alter levels of orexigenic hormones along with early olfactory responses to food odors.* Our setup allows us to deliver appetizing food odors to human subjects undergoing fMRI scanning, and thereby to measure responses to these stimuli in olfactory cortex (i.e., piriform) as well as in reward-related regions (amygdala, orbitofrontal cortex).

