## STUDY ENDPOINTS:

### Primary endpoints

The primary endpoints of this proposal are the analysis of neural representations of high-caloric food odors in early olfactory cortex and food reward regions, and levels of orexigenic hormones using the serial blood samples.

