## Multivoxel pattern analysis

We implemented a searchlight-based multi-voxel pattern analysis (MVPA) (Howard & Kahnt, 2018; Kahnt, Grueschow, Speck, & Haynes, 2011) to decode information about food vs. non-food odors. We first estimated general linear models (GLM) for each subject, separately for each session, using the non-normalized and un-smoothed functional images. The GLM included three regressors of interest specifying onset times for the following conditions: 1) food odors, 2) non-food odors, 3) clean air. We also included the following nuisance regressors: the smoothed and normalized respiratory trace, down-sampled to scanner temporal resolution (0.5 Hz); the 6 realignment parameters (3 translations, 3 rotations), calculated for each volume during motion correction; the derivate, square, and the square of the derivative of each realignment regressor; the absolute signal difference between even and odd slices, and the variance across slices in each functional volume (to account for fMRI signal fluctuation caused by within-volume head motion); additional regressors as needed to model out individual volumes in which particularly strong head motion occurred (absolute difference between odd and even slices >5 SD or slice variance >4 SD). The parameter estimates from the first two regressors of this GLM reflect the voxel-wise response amplitudes for food and non-food odors, separately for each run and sleep session.

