Next, we used these voxel-wise parameter estimates in a searchlight-based, leave-one-run-out cross-validated decoding approach. We decoded food vs. non-food odors from patterns of odor-evoked activity, separately for each of the two sleep sessions. We used The Decoding Toolbox (TDT) to implement the searchlight (Hebart, Gorgen, & Haynes, 2014) and LIBSVM (Chang & Lin, 2011) for the linear support vector machine (SVM) classifier. To test for brain regions that encoded food vs. non-food odors, at each searchlight (sphere with 8 mm radius), we trained a SVM to discriminate between activity patterns evoked by food vs. non-food odors in three of the four runs per session (DS or NDS), and tested it on activity patterns evoked by food vs. non-food from the fourth “left out” run of the same session. The procedure was repeated four times leaving a different run out, and decoding accuracies were averaged and mapped to the center voxel of the searchlight. This procedure was repeated for every voxel within a 10% gray-matter mask (based on SPMs tissue probability map that was inverse-normalized into the individual native space, as described in (Howard & Kahnt, 2018)). The resulting accuracy maps for food vs. non-food odors for DS and NDS sessions were subtracted (DS > NDS), normalized, and smoothed (6mm FWHM). We tested for significant differences between DS and NDS sessions at the group level using voxel-wise one-sample t-tests. Statistical thresholds were set to  $P < 0.05$ , family-wise error (FWE)

small-volume corrected for multiple comparisons at the voxel-level in a functional mask of piriform cortex that was obtained from a one-sample t-test of decoding accuracy for food vs. non-food odors, averaged across sleep sessions.

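### The only specified sleep contrast for the neural endpoint tests food/non-food separability, not whether the food-odor response rises as Aim 1 predicts

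*SAP*

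**What the plan says.** The protocol's Aim 1 gives the neural prediction a direction: "We hypothesize that fMRI responses to high-caloric food odors will be elevated when subjects are sleep-deprived". The Primary endpoints section is less specific and names "the analysis of neural representations of high-caloric food odors in early olfactory cortex and food reward regions". The Purpose announces "pattern-based data analysis to test the effects of sleep deprivation on neural responses to food".

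In the SAP section Multivoxel pattern analysis, the first-level model has three conditions of interest: "1) food odors, 2) non-food odors, 3) clean air". Two of them go forward: "The parameter estimates from the first two regressors of this GLM reflect the voxel-wise response amplitudes for food and non-food odors". From these, the SAP says, "We decoded food vs. non-food odors from patterns of odor-evoked activity, separately for each of the two sleep sessions". The session comparison is then "The resulting accuracy maps for food vs. non-food odors for DS and NDS sessions were subtracted (DS > NDS), normalized, and smoothed", followed by a one-sample t-test at each voxel with family-wise correction inside a piriform mask. Whether the t-test is one- or two-sided is not stated. The mask comes from a group test of food/non-food decoding accuracy averaged over the two sessions.

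The SAP's pre-processing section prepares smoothed, normalized images for connectivity and univariate analyses that it says are described further on. No univariate section follows in the SAP as supplied, and no specified contrast uses the clean-air estimate.

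**The concern.** Aim 1 concerns one odor class, food, and one direction, up. The planned statistic depends on the difference between two odor classes and has no direction in the sense of Aim 1: accuracy rises whenever the two patterns move apart, whichever of them moved and whether its response grew or shrank.

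A significant result therefore would not establish that the food response changed, and a null result would not rule out that it rose. The condition that could separate these cases, clean air, is delivered and modelled but enters no test. At stake is whether the main neural result can be read as an answer to Aim 1.

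**Working it through.** The documents give no effect size, variance or power for this contrast, so there is no planned figure to reproduce. The check concerns what the statistic responds to.

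**Step 1: algebra.** Let f and h be the food and non-food patterns at a searchlight, and D = f − h. A linear classifier scores a test pattern x as w·x + b, with w built from differences between training patterns.

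- *Food moves by δ:* D becomes D + δ. *Non-food moves by −δ:* D becomes D + δ. The separation is the same in both cases.
- *The same pattern k is added to both classes in every run:* D and w are unchanged, b becomes b − w·k, and every score is unchanged. Accuracy cannot move. A numerical check with identical noise gave a maximum accuracy difference of 0.0 over 300 simulated subjects.
- *Both responses are multiplied by g:* D becomes gD against the same noise, so accuracy rises.

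**Step 2: simulation of the SAP procedure at one searchlight.**

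Inputs from the documents: 40 enrolled with 15–25% drop-out, so 40 × 0.85 = 34 and 40 × 0.75 = 30 completers; four runs per session; leave-one-run-out linear SVM; an 8 mm sphere, which holds 257 voxels at 2 mm.

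Assumed inputs: voxel noise SD 1, pattern SD 0.15 for each class, common mean response 0.30, two-sided 0.05, no small-volume correction, 300 replicates. At a rejection rate of 35% the simulation error is √(0.35 × 0.65 / 300) ≈ 2.8 percentage points.

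The root-mean-square food/non-food difference per voxel is √(0.15² + 0.15²) = 0.212 at baseline. It becomes √(0.225² + 0.15²) = 0.270 when either class's pattern grows by half, √(0.045 + 0.15²) = 0.260 when either class's mean shifts by 0.15, and g × 0.212 under a shared gain g.

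| Change under deprivation | RMS difference, before → after | Accuracy, rested → deprived (n = 30) | Rejects, n = 30 / 34 |
|---|---|---|---|
| None | 0.212 → 0.212 | 0.656 → 0.652 | 5% / 4% |
| Food pattern ×1.5 only | 0.212 → 0.270 | 0.650 → 0.735 | 36% / 37% |
| Non-food pattern ×1.5 only | 0.212 → 0.270 | 0.654 → 0.732 | 30% / 37% |
| Food mean +0.15 only | 0.212 → 0.260 | 0.651 → 0.717 | 22% / 27% |
| Non-food mean +0.15 only | 0.212 → 0.260 | 0.647 → 0.715 | 22% / 26% |
| Non-food mean −0.15 only | 0.212 → 0.260 | 0.650 → 0.715 | 21% / 26% |
| Both means +0.15 | 0.212 → 0.212 | 0.654 → 0.653 | 6% / 6% |
| Both means +0.30 | 0.212 → 0.212 | 0.654 → 0.650 | 5% / 4% |
| Both ×1.25 | 0.212 → 0.265 | 0.650 → 0.724 | 29% / 31% |
| Both ×1.5 | 0.212 → 0.318 | 0.653 → 0.801 | 81% / 87% |

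**Step 3: direction.** Suppose the non-food mean starts 0.20 above food (0.50 against 0.30) and food rises to meet it. The difference falls from √(0.045 + 0.20²) = 0.292 to 0.212, and accuracy falls from 0.77 to 0.65. The test then rejects in the deprived-below-rested direction in 60% / 62% of trials, although the food response has risen as Aim 1 predicts.

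**Step 4: a second model, for sensitivity to assumptions.** This used 32 completers (40 × 0.80), 50 pattern dimensions, one odor-general and one class-specific component (SD 0.32 each), noise SD 1 and a nearest-centroid classifier. The planned test rejects in 59% of trials when only the non-food-specific pattern grows by half and in 38% when it halves. It rejects in 4% when only the shared component grows by half, and in 53% and 99% when the whole response to every odor is scaled by 1.25 and 1.5. Food-versus-air decoding rejects in 5–6% under the non-food-only changes and in 61% when the shared component grows by half.

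**Step 5: the amplitude contrast.** A paired session test of food minus clean air stays at 5% when only non-food moves. For a true food change of standardized size dz, power follows a noncentral t with n − 1 degrees of freedom and noncentrality dz√n (for dz = 0.5: 2.74 at n = 30 and 2.92 at n = 34). At n = 30 / 34, power is 36% / 40% for dz = 0.3, 75% / 81% for 0.5 and 99% / 99.5% for 0.8. These dz values are assumed.

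**The case against.** The best defense is that the plan does what the protocol announced. The Purpose names pattern-based analysis, the endpoint concerns representations rather than amplitude, and the Background hypothesis says only that responses are altered. Decoding is an ordinary way to study representations. All of this stands, and it confines the mismatch to Aim 1's prediction of elevated responses.

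Second, the non-food odors are described as controls. A control odor removes changes in general odor detection, sniffing or arousal, which clean air cannot do, so insensitivity to a shared additive shift may be intended as specificity. That is reasonable, though the SAP does not say so. A specificity claim also needs evidence that the food side moved, and this contrast does not supply it.

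Third, a reader might infer that the test would miss any rise common to all odors, including the hormone-driven change in olfactory sensitivity raised in the Background. The documents do not support this. A change in sensitivity reads at least as naturally as a proportional gain, and a shared gain raises accuracy and is detected. Only an equal additive shift is invisible. The gain case raises the opposite difficulty: a rejection that is not specific to food.

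Fourth, nothing in the documents makes a non-food-only change of 50% likely, and the SAP nowhere says that a difference will be reported as a food-only effect. Both are fair limits on the concern.

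**Conclusion.** The point holds as a mismatch between the specified test and Aim 1. The contrast measures a change in food/non-food separability. It rejects about as often for a non-food-only change as for the same food-only change, it also rejects for a shared gain, and it carries no sign for a rise. Its blindness to an equal additive rise in both classes is exact.

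The simulated rates are illustrative. For a non-food pattern grown by half they range from 30% to 59% across the two models, and both models omit the SAP's small-volume correction. The conclusion about what the statistic measures does not depend on them.

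Two stronger readings should be avoided. The SAP does not label this test primary; it is the only specified session test of the primary neural endpoint. Nor is decoding the wrong method for that endpoint: the existing result remains interpretable as selectivity. What it cannot do alone is support or refute a raised food-odor response.

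**What to change.** 1. In the SAP, write out the univariate analysis that the pre-processing section announces: signed deprived-minus-rested tests of food minus clean air and of non-food minus clean air, plus the odor-class-by-session interaction. Use an anatomical piriform mask. The current mask selects voxels that already separate food from non-food, so voxels responding equally to both tend to fall outside it.
2. Food-versus-air and non-food-versus-air decoding maps can be added in support, since a pattern can change without a net change in amplitude. Decoding accuracy is unsigned, so these maps cannot replace the amplitude tests as evidence of a rise.
3. Describe the existing decoding result as a change in food/non-food selectivity, and attribute a sleep effect to food odors only if the food-versus-air contrast changes.
4. State where the food-versus-air test sits in the testing order, for example tested first or with alpha split.

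The cost is SAP wording and analysis time; the clean-air condition is already collected and modelled. The downsides are one more test to place in the hierarchy, and that food versus air also contains general odor detection, which the non-food-versus-air contrast is there to show.

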**MULTI-SITE RESEARCH: N/A**

**STUDY TIMELINES:**

Each participant will follow a ~ 6 week within-subject, crossover partial sleep-deprivation protocol to test the effect of sleep deprivation (SD) and non-sleep deprivation (NSD) on neural processing of food odors in sensory and reward related regions (**Fig. 2**). Qualified subjects will be randomly assigned to either participate in the SD or the NSD condition first. Subjects will then undergo a week of sleep stabilization phase to stabilize circadian rhythms for a week. After the sleep stabilization week, the night before the fMRI session, subjects will either sleep normally (NSD, 8 h of sleep between 11 pm and 7 am), or sleep only for 4 h between 1 am and 5 am (SD) at home. All subjects will participate in both sleep conditions (SD and NSD) in randomized order, separated by ~2.5 week washout period. The

evening of the sleep manipulation, subjects will visit the lab to consume dinner and pick up their sleep monitors. We will also provide a take-out breakfast and lunch to be consumed at 8:00 am and 12 noon, respectively. All meals will be provided by the CRU. Subjects will perform an odor-rating task inside the MRI scanner on the same evening. Serial blood samples will be collected for measurement of appetite-regulating hormones. At the completion of the fMRI scan, participants will be provided with snacks in a buffet-style setting where they will have *ad libitum* access to food items corresponding to the odors used during fMRI scanning (sweet and savory high-calorie snacks). They will be instructed to consume as much food as they like. We anticipate to enroll all participants within a 12-month period and plan to complete the study data collection and analyses within a period of 3 years from the date of IRB approval.

**Figure 2. Study design and scanning protocol. A.** Timeline of the sleep-deprivation protocol. All subjects will participate in both sleep conditions (SD and ND), in randomized order. On the scanning day, blood (BD) will be drawn every 30 min. **B.** For each subject, two sweet and two savory high-calorie food odors will be selected and presented during the scanning session, in addition to two non-food odors and trials in which non-odorized air is presented. **C.** Example trial of the fMRI task. After a countdown, an odor is presented, after which subjects have to rate the pleasantness or the intensity of the delivered odor.

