*fMRI scanning protocol.* On the first day of the study, before being assigned to the SD or NSD phase, subjects will rate the pleasantness of six food odors, including three high caloric sweet (caramel, yellow cake, ginger bread) and three high caloric savory odors (potato chips, pot roast, garlic butter). Based on each participant's ratings, we will select two sweet and two savory odors matched in rated pleasantness. We will also include two control non-food odors (fir and celery seed). On the day of fMRI scanning, subjects will arrive at the imaging center at 6 pm and will consume a dinner before entering the scanner. This pre-feeding will satisfy metabolic hunger (i.e., energy requirements), and thus render the fMRI measures more sensitive to sleep-dependent changes in hedonic hunger, i.e., food intake exceeding energy requirements (47). During fMRI data acquisition, odors will be delivered directly to the subject's nose via a MR-compatible olfactometer. Neuroimaging will be performed at the Northwestern University Center for Translational Imaging (CTI) on a state-of-the-art Siemens PRISMA system with a 64 channel head coil, using imaging sequences optimized for signal recovery in olfactory and orbitofrontal cortices (48). Specifically, subjects will perform 4 runs of an odor detection task inside the MRI scanner while blood oxygen-level dependent (BOLD) responses will be acquired with high spatial (2 mm isotropic) and temporal resolution (2000 ms). On each trial, subjects will be cued to sniff, and an odor corresponding to one of the three experimental groups (sweet, savory, non-food) or clean air will be delivered pseudo-randomly. Subsequently, subjects will rate the pleasantness or the intensity (pseudo-randomized) of the delivered odor. Sniffing behavior will be monitored using an MR-compatible breathing belt and a spirometer. A high-resolution anatomical image will be acquired for the purpose of spatial normalization and anatomical localization of the fMRI responses.

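### The food versus non-food decoding holds out runs but never odors, so it measures discrimination of these particular odor sets and cannot by itself support a food-specific reading

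*SAP*

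**What the plan says.** The protocol's Study Timelines section (Figure 2 legend) sets out the odors used per participant: "two sweet and two savory high-calorie food odors will be selected and presented during the scanning session, in addition to two non-food odors". Procedures Involved fixes the controls: "We will also include two control non-food odors (fir and celery seed", the same for everyone. Matching is stated only within the food set: "we will select two sweet and two savory odors matched in rated pleasantness". In the scanner, "subjects will perform 4 runs of an odor detection task inside the MRI scanner", and after each odor "subjects will rate the pleasantness or the intensity (pseudo-randomized) of the delivered odor".

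The SAP section Multivoxel pattern analysis models the odors by category only: "The GLM included three regressors of interest specifying onset times for the following conditions: 1) food odors, 2) non-food odors, 3) clean air". Neither rated pleasantness nor rated intensity is among its listed nuisance regressors. The classifier step is "we trained a SVM to discriminate between activity patterns evoked by food vs. non-food odors in three of the four runs per session", with testing on the remaining run of the same session. The stated purpose is "To test for brain regions that encoded food vs. non-food odors".

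The deprived and non-deprived accuracy maps are then subtracted and tested with a one-sample t-test. The test is corrected within a piriform mask that is itself defined by the same accuracy, averaged over sessions. Neither document tests an odor that was absent from training, or regroups the six odors as a control.

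**The concern.** Leaving out a run guards against fitting run-specific noise. It does not show that what the classifier learned is shared by food odors. If each odor evokes its own reproducible pattern, the average of four particular odors differs from the average of two others whatever the labels mean. A classifier tested on the same odors will pick up that difference.

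Piriform cortex is the primary olfactory region and the region chosen for the corrected test, so odor-specific patterns are a natural rival explanation there. Subtracting sessions does not remove it. If sleep loss strengthens responses to odors in general, separability rises with no change specific to food. The protocol's Background raises this possibility itself, by suggesting that appetite hormones act through olfactory sensitivity.

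At stake is how a primary endpoint, the neural representation of high-calorie food odors, may be described.

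**Working it through.** The documents give no decoding accuracy, effect size or signal-to-noise figure, so there is no planned number to reproduce.

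**Inputs from the documents.** Four food and two non-food odors; 4 runs per session; a searchlight of 8 mm radius on 2 mm voxels, which is 257 voxels in a full sphere; 40 enrolled with 15-25% dropout, leaving 40 × 0.85 = 34 to 40 × 0.75 = 30 completers.

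**Step 1: class difference with no food code.** Give each odor an independent pattern with variance s² per voxel and nothing shared among food odors. The difference between the two class means has variance s²/4 + s²/2 = 0.75 s². This is not zero and it recurs in every run, so leave-one-run-out accuracy must exceed 0.50 once s² is large enough relative to noise.

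**Step 2: size under assumed signal-to-noise.** One searchlight was simulated with no food code and with noise equalised between the two class means. Two noise scalings were used, so the table also gives pattern SD divided by the noise SD of a class mean:
- Scaling A: single-odor noise 1 for food and 1/√2 for non-food. Both class means have noise √(1/4) = 0.50.
- Scaling B: single-odor noise √2 for food and 1 for non-food. Both class means have noise √(1/2) = 0.71.

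| Scaling, classifier | Pattern SD | Ratio to class-mean noise | Planned accuracy | Accuracy on held-out odors |
|---|---|---|---|---|
| A, linear SVM | 0.10 / 0.15 / 0.20 | 0.20 / 0.30 / 0.40 | 0.60 / 0.72 / 0.83 | 0.50 throughout |
| B, least-squares linear | 0.1 / 0.2 / 0.3 | 0.14 / 0.28 / 0.42 | 0.55 / 0.70 / 0.86 | 0.50 throughout |

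On the common ratio scale the two sets agree. With no signal at all, both methods give 0.50.

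**Step 3: the session difference.** This uses scaling B, pattern SD 0.2, 30 subjects and no food code. If odor responses are 1.3 or 1.5 times stronger in the deprived session (assumed), planned accuracy rises by 0.10 or 0.18. The change on held-out odors is 0.01 or less. With equal responses in both sessions, the planned difference test is positive in about 3-6% of simulated studies, close to its nominal rate.

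**Step 4: which cross-odor pairs to use.** Train on one food odor against one non-food odor, and test on a different food odor against the other non-food odor. This gives 4 × 3 × 2 = 24 combinations. Of these, 4 × 1 × 2 = 8 stay within sweet or within savory and 4 × 2 × 2 = 16 cross between them. Suppose sweet odors share a pattern and savory odors share another, still with no food code (identity SD 0.15, shared SD 0.15-0.20, assumed). Accuracy over all 24 is then about 0.53 to 0.58, depending on the classifier. Over the 16 crossing combinations it is about 0.50. Only the 16 avoid mistaking sweet or savory quality for food.

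**The case against.** The strongest reply is that the SAP promises no abstract food code. Its purpose statement concerns a contrast between two odor sets, the endpoint concerns representations of food odors, and the pattern of an individual food odor is such a representation. The session comparison is randomised and within subject, so a positive result reflects a real effect of sleep on how separable these odors are. All of this stands. A reader might infer that the SAP claims a region encodes food as such, or that its primary neural test is invalid. The wording supports neither.

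A reader might also take the positive results in Step 3 for false positives. At one uncorrected voxel, the planned test is positive in 53% and 95% of simulated studies at gains of 1.3 and 1.5. Those simulations build in a real change in odor patterns, so the percentages are sensitivity to that change, not type I error. Nor do they describe the SAP's test, which applies voxel-level family-wise correction to smoothed maps.

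Two further points are fair. Neither document says outright that every odor occurs in every run. And cross-odor decoding can still succeed on pleasantness or intensity that the food odors share, because matching is stated only among them.

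What the reply does not remove is the ambiguity. The protocol's hypotheses concern food odors and food stimuli, so readers will tend to take the result as food-specific, and the planned analysis cannot separate that from odor identity. Letting food odors differ between subjects does not help, because decoding is within subject.

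**Conclusion.** The point holds as a limit on interpretation. The planned decoding, and a session difference in it, can arise from odor identity alone. The planned test remains valid for whether sleep deprivation changes the separability of these particular food and non-food odor sets. It cannot alone support a food-specific reading.

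The argument needs only that training and test runs share odors, which is a fair inference from the protocol. The simulated accuracies also assume independent odor patterns, equal class noise and a chosen signal range, none of which the documents supply. They show that the problem can occur and do not estimate its size here.

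**What to change.** Keep the planned map, mask and test unchanged. Add to the SAP section Multivoxel pattern analysis:

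1. A supporting first-level model with one regressor per odor (six odors plus clean air).
2. A cross-odor map. Train on one food odor against one non-food odor in three runs. In the left-out run, test on a food odor of the other quality against the other non-food odor. Average over the 16 sweet-to-savory and savory-to-sweet combinations, with each run left out in turn.
3. The same deprived-minus-non-deprived test, with the same family-wise error rule, in the same mask.
4. A reporting rule. The planned result is described as discrimination of these food and non-food odor sets. A food-category interpretation is made only if the cross-odor result supports it, and with the note that pleasantness or intensity shared by the food odors could still contribute.

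This needs no new data, only SAP wording and analysis time. The plan should confirm that each odor occurs in each run. The downside is sensitivity: per-odor estimates use fewer trials and are noisier, and only two non-food odors are available. In one simulated case with a true food code, cross-odor accuracy was about 0.57 against 0.63 for the planned method. A null supporting result would therefore not show that a food code is absent. If the added map is declined, the wording limit in item 4 can still be adopted, with no food-category interpretation made.
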